In Task 1, a convenience sample of five participants will be recruited for CNN model training. For each patient, we plan to collect data for 2.8 hours, among which at least 17 minutes will be FoG data. Each participant will be asked to wear one UG motion sensor (watch like device with a soft band) around each ankle to collect raw data that will be used to detect FoG and develop models. They will be video-taped (for the purpose of validating the FoG detection models) as they walk each of the five 5-meter FoG triggering courses illustrated in Figure 1. All assessments in Task 1 will be performed on PD participants who are OFF their PD medications (overnight washout) to maximize the amount of time spent in FoG, thereby minimizing the length of evaluation time [19]. It is common in both clinical practice and research studies to bring PD patients in for assessments off their PD medications; thus, this is not anticipated to be a barrier to recruitment. The 6 participants in Task 1 will not participate in Task 2 & 3.

Task #1: Each subject is expected to spend up to 4 hours in the clinical lab, one visit. This can be divided into two sessions if the subject prefers.

[figure not shown]

Figure 1: Five FoG Triggering Scenarios shall include a 5-meter walking path with one of 5 triggers inserted into the path: (A) walking through a narrow passage, (B) turning 540 degrees, (C) approaching a destination (e.g., chair), (D) walking while dual tasking (e.g., performing a verbal fluency challenge while walking), and (E) a time sensitive task such as walking through an elevator door before it closes.

Table 2. Task 2 Neuropsychological Scales (total participant time for all the below measures is 88 to 118 minutes).

Anxiety	State Trait Anxiety Inventory (STAI- State & Trait) [9] Positive and Negative Affect Schedule (PANAS-State) [10] Semi-structured qualitative interview Salivary Alpha-Amylase [11-13]
Sleep	RegUlarity, Satisfaction, Alertness, Timing, Efficiency, and Duration (RU SATED) [14] Insomnia Severity Index (ISI) [15] Pittsburgh Sleep Quality index (PSQI) [16] Actigraph Consensus Sleep Diary [17]
Self-Efficacy	General Self-Efficacy Scale (GSE) [18]
Illness Self-Concept	Illness Self-Concept Scale (ISCS) [19-20]

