The goals of **Task 2** are to (1) determine the optimal frequency and vibration settings to mitigate freezing of gait (FoG) and (2) explore the role of neuropsychological factors such as sleep and anxiety in FoG outcomes (see Table 1 & 2). Thus, response surface methodology is proposed. Specifically, a central composite design (CCD) [38] will be used to determine the best dose of vibration (frequency and amplitude) for each of five common triggers for FoG (Figure 1). Estimating the response surface requires only a small sample of human participants, e.g., one participant for each design point with five repeats at the center point. For the current project, a convenience sample of only 13 participants with PD who experience FoG in at least two of the scenarios, confirmed by a neurologist will be needed. The 13 participants will be asked to walk through each of five, 5-meter walking courses that will each include one of the triggering scenarios. Each of the 13 PD participants with FoG will be randomly assigned to one of 9 different *ff* and *va* settings as prescribed by the CCD. In the current case, the goal is to estimate the *ff* and *va* settings that will maximize the difference between the baseline (no vibration) and post-treatment time spent in a FoG state for each of the 5 triggering scenarios individually and in total. Measurements will be taken once at baseline and again in triplicate as they walk the paths wearing the FoG detection/vibration device.

Additional activities for Task 2 participants:

Visit #1: After the consenting process is completed, a sample of saliva will be collected (see procedure below) to measure salivary alpha amylase levels at baseline. The UG device and PDVibe3 will be placed on the participants who will then perform a 10-meter walk test on site and a baseline walk of the five triggering

scenarios. They will complete the questionnaires/scales listed in tables 1 and 2. Participants will then be instructed on how to wear the actigraph device on their dominant wrist (Actigraph GT9X Link) to collect objective sleep data for up to 14 days prior to their Visit #2. They will also be instructed on how to complete the sleep diary during the same time period during which the actigraph is collecting sleep data. Visit #1 will last approximately 90 minutes.

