Participants will wear the ActiGraph GT9X Link for up to 14 consecutive, 24-hour days beginning at baseline, pre-intervention. Actigraphs are devices that are worn on the dominant wrist and contain a built-in accelerometer that records movements in order to estimate sleep parameters, including total sleep time, sleep-onset latency, wake after sleep onset, and sleep efficiency. Sleep data will be analyzed using the ActiLife 6.0 data analysis software platform and bedtime and waketime will be verified via sleep diary-reported data. Prior to receiving the actigraph, participants will receive verbal instructions regarding the purpose of the actigraph (i.e., that the actigraph records movement to estimate sleep parameters) as well as appropriate use (i.e. should be worn on the dominant wrist at all times for up to fourteen consecutive days unless bathing, swimming, etc.). Participants will be provided with moleskin as necessary to minimize risk of skin abrasion. Participants will be encouraged to reach out to study personnel with any questions or concerns related to wearing the actigraph device while at home.

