Participant saliva will be collected with the aim to assess salivary alpha amylase, a biomarker shown to be a reliable indicator of anxiety and stress in individuals with PD. Saliva sample collection will occur three times over the course of Task 2- at baseline (Visit #1), pre walking tasks and post walking tasks (Visit #2). Saliva will be collected using a passive drool method, a method of saliva collection that requires participants to lean forward and allow saliva to naturally pool into the collection vessel rather than actively spitting. This method of saliva collection allows for whole saliva to be collected, avoiding localized salivary secretions and providing for a more consistent biospecimen. Saliva samples will be collected utilizing Salimetrics Saliva Collection Aid, a mechanism which fits securely into a collection vial designed to reduce sample foaming and facilitates direct sample collection and storage. Samples will be refrigerated within 30 minutes of initial collection and frozen at or below -20 degrees Celsius within 4 hours of collection. Samples can be stored for up to 6 months and will be stored until all participant samples are collected, at which point an alpha amylase assay will be run. Prior to participating in saliva collection, participants will receive verbal instructions on how to correctly provide a saliva sample. Participants will be advised to avoid eating a major meal for at least one hour and will be asked to rinse their mouths thoroughly with water 10 minutes prior to collection.

Visit #2: In addition to what is described in Task #1 above, saliva samples will be collected from participants before and after their participation in the walking tasks. They will also complete 2 surveys, the STAI-State and PANAS-State after they finish walking. The sleep diary that was filled out at home will be collected from participant and actigraphy will be retrieved. Following completion of walking tasks, participants will be invited to schedule a time to engage in a semi-structured qualitative interview virtually or by phone. Visit #2 will last approximately 120 to 180 minutes).

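### Task 2 appears to take its no-vibration baseline at Visit #1 and its vibration walks on a later day; a same-day baseline at Visit #2 would cheaply remove between-day noise

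*Protocol*

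**What the plan says.** **Response.** The Task 2 paragraph of protocol section 4.2.a aims to find the settings that "maximize the difference between the baseline (no vibration) and post-treatment time spent in a FoG state". The schedule there is: "Measurements will be taken once at baseline and again in triplicate as they walk the paths wearing the FoG detection/vibration device". SAP section 3 defines the modelled response as baseline minus the average of the three vibration trials.

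**Visit #1.** After the devices are fitted, participants "perform a 10-meter walk test on site and a baseline walk of the five triggering" scenarios. They then take home an actigraph to "collect objective sleep data for up to 14 days prior to their Visit #2". The actigraphy paragraph describes the wear period as "up to 14 consecutive, 24-hour days beginning at baseline, pre-intervention".

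**Visit #2.** Saliva is taken "at baseline (Visit #1), pre walking tasks and post walking tasks (Visit #2"), which sets baseline and walking tasks at different visits. The visit itself is introduced with "Visit #2: In addition to what is described in Task #1 above, saliva samples will be collected from participants before and after" the walking tasks. No no-vibration walk is named there.

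**Medication state.** For Task 1: "All assessments in Task 1 will be performed on PD participants who are OFF their PD medications (overnight washout"). The protocol puts Task 2 participants ON medication. It sets no time since last dose for Task 2. The SAP lists timing of the last dose among the Task 1 descriptors but not among those for Task 2.

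**SAP schedule.** SAP section 5, which is the 2020 grant text, has Task 2 done in a single 2-hour session. The 2023 protocol has three visits.

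**The concern.** The response was defined when all Task 2 walking was to happen in one session. With the walking apparently spread over two visits, subtracting vibration walks from baseline no longer compares like with like within a day. Whatever changes in a participant's freezing between the visits enters the response together with the vibration effect. The protocol itself treats sleep and anxiety as possible influences on freezing, and both can differ between days, as can time since the last dose.

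Each participant receives one setting and contributes one response per outcome, so the 13-run fit cannot separate this change from vibration. The fitted frequency and amplitude are programmed into the device for Task 3. Under the contingency plan in SAP section 3, a scenario without an identified optimum goes to the highest tolerated dose, so a noisier fit could change what participants receive in Task 3.

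The Task #1 pointer compounds the problem. Taken literally it calls for OFF-medication walks without vibration, which conflicts with the ON rule, and it leaves site staff without a written walking sequence for Visit #2.

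**Working it through.** **1. The plan's own design.** Runs: 2² factorial + 2×2 axial + 5 centre = 13, at 4 + 4 + 1 = 9 settings. Axial points at distance √2: 225 ± 50×1.414 gives 154.29 and 295.71; 0.65 ± 0.10×1.414 gives 0.509 and 0.791. These match SAP section 3. The second-order model has 6 coefficients, leaving 13 − 6 = 7 residual df.

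**2. A shift common to all participants.** Adding 1 to all 13 responses and refitting changes the coefficients by (1, 0, 0, 0, 0, 0). The shift goes wholly into the intercept. The estimated mean benefit is biased and the estimated optimum does not move.

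**3. Change that differs between participants.** The documents give no variance components, so these are assumptions:
- s = walk-to-walk SD within a day;
- t = day-to-day SD of a participant's level, independent between visits;
- h = SD of true benefit between people.

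For baseline minus the mean of three:
- same day: Var = s²(1 + 1/3) + h²;
- different days: Var = s²(1 + 1/3) + h² + 2t².

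Settings are randomised, so the extra 2t² is noise and not expected bias in the optimum. Every coefficient's standard error rises by the same ratio as the response SD. The half-width for mean benefit at the design centre is 2.365 × √(0.20 × Var), where 0.20 is the leverage at the centre and 2.365 is t(0.975) on 7 df.

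| h | t/s | Var (s²) | SD ratio | Between-day share of Var | 95% half-width at centre (s) |
|---|---|---|---|---|---|
| 0 | same day | 1.333 | 1 | 0 | 1.22 |
| 0 | 0.5 | 1.833 | 1.17 | 27% | 1.43 |
| 0 | 1 | 3.333 | 1.58 | 60% | 1.93 |
| 1 s | same day | 2.333 | 1 | 0 | 1.62 |
| 1 s | 0.5 | 2.833 | 1.10 | 18% | 1.78 |
| 1 s | 1 | 4.333 | 1.36 | 46% | 2.20 |
| 2 s | same day | 5.333 | 1 | 0 | 2.44 |
| 2 s | 0.5 | 5.833 | 1.05 | 9% | 2.55 |
| 2 s | 1 | 7.333 | 1.17 | 27% | 2.86 |

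The rows with h = 0 are an extreme case, since they assume everyone benefits equally.

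**4. Finding an optimum.** Simulated fits on an assumed surface with its peak at coded (0.25, 0.25). The figures are the share of fits whose stationary point is a maximum inside the design region (radius √2), for same day, then t/s = 0.5, then t/s = 1. They are good to about 1 percentage point.

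| Curvature (s per coded unit²) | h = 1 s | h = 2 s |
|---|---|---|
| −0.5 | 39 / 36 / 30% | 27 / 27 / 25% |
| −1 | 72 / 67 / 55% | 50 / 48 / 43% |
| −2 | 98 / 97 / 91% | 86 / 84 / 79% |

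The loss against the same-day column runs from about 0 (27 − 27) to 17 points (72 − 55).

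**The case against.** The strongest reply is that the split is inferred and that other text points the other way.

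- The visit descriptions are headed as activities additional to the core Task 2 sequence. If Task #1 is a slip for Task #2, Visit #2 imports that whole sequence, perhaps including a no-vibration walk.
- Taken literally, the pointer imports the Task 1 walks, which are also without vibration.
- The Visit #1 walk may serve eligibility, since freezing must be observed in at least two scenarios.
- Task 3 replacements do the Task 2 baseline walking at a separate visit and still make a no-vibration pass in Task 3. A walk called baseline is therefore not always the comparator.
- The SAP's single session suggests that a same-day comparison was intended.
- The protocol text is an extract, so its silence is weak evidence.

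These points stand as reasons for caution. They do not settle the matter for the plan. A single baseline measurement, a named baseline walk at Visit #1 and a saliva schedule that contrasts baseline with the walking tasks still favour the split. If a same-day walk was intended, there are two candidate baselines and nothing says which enters the response. The literal pointer brings in the wrong medication state. Every reading needs a correction.

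It is also fair that the main aim of Task 2 is the optimum, not the mean benefit, that Task 3 makes its own before-and-after comparison, and that a fallback dose exists. These limit the consequence. If benefit varies widely between people, having one person at each of the eight non-centre settings is the larger limitation, and the gain from a same-day baseline is small.

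**Conclusion.** The point holds as a cheap improvement. On the best-supported reading, the Task 2 response mixes between-day change with vibration, and the Visit #2 text needs correcting on any reading.

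The size depends on assumptions. With t/s of 0.5 to 1 and h of 1 to 2 s, response SD and coefficient standard errors rise 1.05 to 1.36 times, and interior maxima become less frequent by about 0 to 17 points depending on curvature. More scenarios would then go to the fallback dose.

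A reader might infer four stronger things that the documents do not support:
- That the split is stated. No sentence places the vibration walks only at Visit #2.
- That the visits are 14 days apart. That figure is the maximum actigraph wear; no visit interval is set.
- That OFF-medication walks are compared with ON-medication walks. The ON rule covers Task 2, and the Task #1 pointer may be a slip.
- That the optimum is biased. A common shift leaves it in place, and with randomised settings individual change adds noise only.

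**What to change.** Replace the Task #1 reference at Visit #2 with the Task 2 sequence: ON medication, one no-vibration walk of each course, then three vibration walks of each. Name that same-day walk as the baseline in the response. Keep the Visit #1 walk for eligibility, familiarisation and description. Record the time of the last dose at Visit #2. Task 3 already uses this order of walks. If the Visit #1 baseline is deliberate, say so and set a visit interval.

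**Cost.** Vibration walks number 3 × 5 = 15 per participant; five more makes 20, or 5 × 13 = 65 extra 5-metre walks in all. There are none if a same-day walk was already intended. Add slightly more fatigue before the vibration walks, one data field and a wording amendment.

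**What it does not cure.** The no-vibration walk always comes first, so practice, fatigue and time since dose within the session stay mixed with vibration. With either baseline, the mean change should not be attributed to vibration alone.

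### No self-reported state-anxiety score is scheduled before the walks of the same visit in Task 2, so the direction of a same-day association with freezing is unclear

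*Protocol*

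**What the plan says.** Protocol 4.2.a gives Task 2 two goals. The second is to "explore the role of neuropsychological factors such as sleep and anxiety in FoG outcomes (see Table 1 & 2"). The Anxiety row of Table 2 lists "State Trait Anxiety Inventory (STAI- State & Trait"), PANAS-State, a semi-structured interview and salivary alpha-amylase.

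- **Visit #1.** The account opens with "After the consenting process is completed, a sample of saliva will be collected". The devices are then fitted and participants "perform a 10-meter walk test on site and a baseline walk of the five triggering" scenarios. The next sentence is "They will complete the questionnaires/scales listed in tables 1 and 2". No order word ties that sentence to the walks.
- **Between visits.** Actigraphy and a sleep diary run for up to 14 days.
- **Visit #2.** Saliva is taken before and after the walks. For self-report, the text is "They will also complete 2 surveys, the STAI-State and PANAS-State after they finish walking".

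The saliva schedule is restated as three samples: "at baseline (Visit #1), pre walking tasks and post walking tasks (Visit #2").

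Neither document gives an analysis model, test or significance level for anxiety and FoG. The SAP is the 2020 grant text and does not include the Table 2 scales, so its silence on anxiety reflects its date.

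**The concern.** A state scale records how the person feels at the time of completion. If it is completed just after a set of walks designed to provoke freezing, a participant who froze more may score higher because of the freezing. A participant who was more anxious beforehand may also freeze more. A post-walk score correlates with FoG under either account.

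The plan already samples the biomarker on both sides of the Visit 2 walks but does not do so for the matching self-reports. At stake is how an association between STAI-State or PANAS-State and FoG would be read. It could be reported as anxiety contributing to freezing when the collected order fits the reverse equally well.

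**Working it through.** **Step 1. Place each state measure in time.** Inputs are Protocol 4.2.a, Task 2, Table 2 and the Visit #1 and Visit #2 paragraphs, with Visit 1 read in the order in which it is written.

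| Task 2 time point | STAI-State and PANAS-State | Salivary alpha-amylase |
|---|---|---|
| Visit 1, before baseline walks | none | yes |
| Visit 1, after baseline walks | yes | none |
| Visit 2, before vibration walks | none | yes |
| Visit 2, after vibration walks | yes | yes |

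Self-report: 1 + 1 = 2 administrations, of which 0 precede the walks of the same visit. Saliva: 1 + 2 = 3 samples, of which 2 do. The saliva count matches the three samples that the Protocol states. The Visit 2 entries are explicit. The Visit 1 entries rest on narrative order.

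**Step 2. Ask whether the Visit 1 self-reports fill the gap.** They precede every Visit 2 walk whatever the order within Visit 1. Three limits remain.

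- The score may be up to about 14 days old, so it is not state anxiety at the time of the Visit 2 walks.
- As listed, it follows the Visit 1 trigger walks. Someone who froze at Visit 1 may score high for that reason and freeze again at Visit 2.
- The walk without vibration is at Visit 1, while Visit 2 FoG is measured under nine different vibration settings. As listed, the vibration-free FoG outcome has no earlier self-reported state score.

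**Step 3. Precision.** Task 2 has 13 participants. The design size reproduces: 4 factorial + 4 axial + 5 center points = 13. Alpha is assumed to be two-sided 0.05, because none is given for this goal.

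- Critical correlation: t(0.975, 11 df) = 2.201, so |r| = 2.201/√(2.201² + 11) = 0.553.
- 95% interval by Fisher z: tanh(atanh r ± 1.96/√(13 − 3)). For r = 0.5 this is tanh(0.549 ± 0.620), or −0.07 to 0.82.

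Suppose freezing alone produced a correlation r with later state anxiety. The values of r are assumed, since the documents give none. By simulation, the chance of p < 0.05 would be:

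| Assumed r | Chance of p < 0.05 | 95% interval if r is observed |
|---|---|---|
| 0.3 | about 17% | −0.30 to 0.73 |
| 0.5 | about 43% | −0.07 to 0.82 |
| 0.7 | about 82% | 0.24 to 0.90 |

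The middle column is simply the power of a correlation test at each assumed r. It shows that a post-walk association could look convincing with no effect of anxiety on FoG. It does not estimate a bias in this trial, and the documents plan no such test.

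**Step 4. After the change.** With a pre-walk administration added at Visit 2 and the Visit 1 scales moved ahead of the walks, self-report occurs three times (Visit 1 pre-walk, Visit 2 pre-walk, Visit 2 post-walk), at the same points as saliva. The intervals in Step 3 hardly move. Adjusting for one covariate, the interval for r = 0.5 is −0.10 to 0.83.

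**The case against.** A reader might infer that state anxiety is measured only after walking, that no state score precedes any walk, and that the second goal therefore cannot be answered. The documents do not support this.

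- Alpha-amylase is in the Anxiety row of Table 2, and the Protocol treats it as a dependable marker of anxiety and stress. It is taken before the walks at both visits, so time order exists for the biomarker.
- The Visit 1 STAI-State, STAI-Trait and PANAS-State scores precede all Visit 2 walks.
- The goal is to explore. It states no direction, hypothesis or test, and the interviews also serve it.
- The sequence within Visit 1 is inferred from the order of sentences.

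All of this stands, and it confines the point to same-day self-report. Saliva does not give a direction to the STAI or PANAS results, and a trait score does not measure state.

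Two further objections have force. Participants are enrolled because they already freeze, so even a pre-walk score may reflect earlier freezing. Also, as listed, the two visits give post-walk scores at matched times, without vibration at Visit 1 and with it at Visit 2. Moving the Visit 1 scales with no post-walk repeat would lose that comparison. The fix allows for this.

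**Conclusion.** The point holds in a narrow form. At Visit 2 there is explicitly no self-reported state-anxiety score before walking. At Visit 1 there is none if the sentences are followed in order. The direction of a same-day association between self-reported state anxiety and FoG is therefore unclear. This limits the second goal of Task 2 without defeating it, because the pre-walk saliva values, the Visit 1 scores and the interviews remain usable for exploration.

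The importance is low. The goal is exploratory, and 13 participants give wide intervals whatever the timing. No figure in the documents sizes the effect of freezing on later anxiety, so the percentages in the working are illustrations that follow from the assumed correlations. The change is worth making because it is cheap and gives the self-report data a time order that they now lack.

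**What to change.** - **Visit 2:** give STAI-State and PANAS-State with the pre-walk saliva sample, and keep the post-walk administration.
- **Visit 1:** state the order of procedures and place the two state scales before the baseline walks. If a post-walk comparison between Visit 1 and Visit 2 is wanted, also keep a post-walk administration at Visit 1.
- **Analysis:** relate pre-walk scores to FoG in the walks that follow, and report pre-to-post change separately. Describe the results as exploratory, with intervals, and say that order in time is not proof of cause.

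The cost is a few minutes (assumed) for two short forms at Visit 2, which is planned at 120 to 180 minutes. Reordering Visit 1 adds no forms. An optional post-walk repeat there would add the same few minutes to a visit planned at about 90. No new instrument or staff is needed.
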